17. STATISTICAL CONSIDERATIONS

17.1. Sample size:

We plan to recruit 30 participants to provide sufficient data to assess progression criteria to inform the decision to move to a definitive randomised Phase III evaluation (WP4). As this study is designed to determine the feasibility of a confirmatory trial and not to assess proof of concept or evaluate effectiveness, formal power calculations are not appropriate

Progression criteria will assess recruitment, follow-up, delivery and acceptability of the intervention using a traffic light system (Table 2). With 30 participants, the 95% CI around our green (go) criteria will exclude values in the red zone, relating to our stopping criteria. Therefore, with 30 patients, should we meet the go criteria we can be sufficiently confident that follow-up, delivery and acceptability will not fall to unacceptable levels as defined by the red (stop) criteria.

Recruitment of 30 participants will take place over four months in four centres, with approximately two to three participants recruited per month per center. With at least two therapists per center, this corresponds to one to two new participants a month per therapist, in line with recruitment and capacity requirements for the planned definitive trial (WP4).

Table 2 Feasibility study progression criteria

	Red	Amber	Green
			(95% CI)
Recruitment : Average no. patients	<4	4-7	>7
recruited / month			

Follow-up: % patients completing	<60%	60-75%	>75%
6m primary outcome			(95% Cl: 59.5%, 90.5%)
Delivery: % therapist delivering	<60%	60-80%	>80%
key intervention components			(95% Cl: 65.7%, 94.3%)
(overall and by each therapy)			
Acceptability: % participants	<50%	50-70%	>70%
attending 1st session			(95% CI: 53.6%, 86.4%)

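### Section 17.1 says the 95% CI at the green criteria excludes the red zone, but Table 2's own follow-up interval reaches 59.5% against a red zone below 60%

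*Protocol*

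**What the plan says.** Protocol section 17.1 sets the recruitment target with this reason: "We plan to recruit 30 participants to provide sufficient data to assess progression criteria". It says that formal power calculations do not suit a feasibility study and rests the number on the precision of the progression criteria instead: "With 30 participants, the 95% CI around our green (go) criteria will exclude values in the red zone, relating to our stopping criteria". From this it concludes that, if the go criteria are met, "we can be sufficiently confident that follow-up, delivery and acceptability will not fall to unacceptable levels as defined by the red (stop) criteria".

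Table 2, in the same section, gives the zones and an interval for each green criterion that is a proportion:

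- Follow-up (completion of the 6-month primary outcome): "Follow-up: % patients completing <60% 60-75% >75" per cent, with "95% Cl: 59.5%, 90.5" per cent.
- Delivery: "Delivery: % therapist delivering <60% 60-80% >80" per cent, with "95% Cl: 65.7%, 94.3" per cent.
- Acceptability (attendance at the first session): "Acceptability: % participants <50% 50-70% >70" per cent, with an interval of 53.6% to 86.4%.

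The recruitment row is a monthly count and carries no interval. Section 17.3 defines the analysis population as all registered participants.

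**The concern.** The sentence on excluding the red zone is unqualified, and the one after it names follow-up. Yet the follow-up row of Table 2 prints a lower limit of 59.5%, and values from there up to 60% are red. The text and the table cannot both be right.

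This property is the only statistical reason given for choosing 30. Follow-up here means completion of the CORE-OM, the proposed primary outcome of the definitive trial, and it is one of four progression criteria. Those deciding on progression are told that a green result makes stop-level follow-up implausible, so that statement should be accurate for each criterion it covers.

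**Working it through.** **Inputs (protocol section 17.1 and Table 2).** n = 30. Green thresholds: 75% (follow-up), 80% (delivery), 70% (acceptability). Red zones: below 60%, below 60% and below 50%.

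**Step 1: reproduce the printed intervals.** Wald 95% interval: p ± 1.96·√(p(1−p)/30).

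| Row | Calculation | Result | Printed | Red | Excludes red? |
|---|---|---|---|---|---|
| Follow-up | 0.75 ± 1.96·√(0.75·0.25/30) = 0.75 ± 0.155 | 59.5% to 90.5% | 59.5% to 90.5% | <60% | No |
| Delivery | 0.80 ± 1.96·√(0.80·0.20/30) = 0.80 ± 0.143 | 65.7% to 94.3% | 65.7% to 94.3% | <60% | Yes |
| Acceptability | 0.70 ± 1.96·√(0.70·0.30/30) = 0.70 ± 0.164 | 53.6% to 86.4% | 53.6% to 86.4% | <50% | Yes |

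All three agree to the printed decimal. The 59.5% is therefore a correct Wald limit, and the error lies in the sentence that describes it. The overlap is 60 − 59.5 = 0.5 points.

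**Step 2: try other 95% methods at exactly 75%.** The lower limits are Jeffreys 57.7%, Wilson 57.3%, Agresti-Coull 57.1%, Clopper-Pearson (exact) 55.9%, and Wald with continuity correction 57.8%. None reaches 60%. A 90% Wald interval (62.0% to 88.0%) does, but the table states 95%.

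**Step 3: use the lowest attainable green count.** Green is strictly above 75%, and 0.75·30 = 22.5, so the smallest green result among 30 is 23/30 = 76.7%.

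- Wald: 0.7667 ± 1.96·√(0.7667·0.2333/30) = 0.7667 ± 0.1514, that is 61.5% to 91.8%. This clears red.
- Wilson: centre (0.7667 + 0.0640)/1.1280 = 0.7364; half-width 1.96·√(0.7667·0.2333/30 + 0.00107)/1.1280 = 0.1457; interval 59.1% to 88.2%. The lower limit is 0.9 points inside red.
- Exact: lower limit is the 2.5% quantile of Beta(23, 8) = 57.7%; upper limit is the 97.5% quantile of Beta(24, 7) = 90.1%. The lower limit is 2.3 points inside red.

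The exact result can be read directly: if true follow-up were 60%, the binomial probability of 23 or more out of 30 is 4.4%, which is above the 2.5% per tail implied by a two-sided 95% interval.

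**Step 4: see how far the method dependence extends.** At 24/30 (80%) the lower limits are 65.7% (Wald), 62.7% (Wilson) and 61.4% (exact), and all clear red. The three methods disagree at one green count only, 23/30.

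**The case against.** The strongest reply is that the printed interval belongs to exactly 75%, which is amber and cannot occur with 30 participants. The operative sentence is conditional on meeting the go criteria. At every attainable green count, from 23/30 upwards, the protocol's own Wald method excludes red. That is correct. A reader might infer from Table 2 that a green follow-up result gives no protection against stop-level follow-up, but the protocol does not support so strong a reading.

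It can also be said that 17.1 names no interval method, that the choice may be left to the analysis plan, and that Wilson or exact is partly a preference. This stands in part. The contradiction at 75% does not depend on that preference, because it appears on the plan's own method. The preference matters only for whether 23/30 clears red.

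Finally, the study is single-arm and descriptive, the zones are defined by percentages, and nothing makes progression depend on a confidence limit. So no traffic-light classification changes. This limits the severity, but it does not make the sentence in 17.1 true: the interval the protocol presents for the green criterion is the one at 75%, and it includes red values.

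**Conclusion.** The stated property is wrong for follow-up and right, on the printed intervals, for delivery and acceptability. The overlap is about 0.5 points on the protocol's own method. At 23/30 the assurance holds with Wald (61.5%) and narrowly fails with Wilson (59.1%) and exact (57.7%); from 24/30 upwards it holds with all three. The assurance for follow-up is therefore marginal and method-dependent at a single count.

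This assumes that 30 participants are registered and that all of them form the follow-up denominator. Severity is minor to moderate: the sentence carries the rationale for the sample size and informs a progression decision, but the numerical gap is small and no recruitment, data collection or classification rule is affected.

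A reader might also infer that the sample size must rise (a Wald lower limit at exactly 75% reaches 60% only at n=33) or that the green bar must move to 24/30. Neither follows. Exactly 75% is not a green result, and raising the bar would alter a pre-specified criterion, which is a trade-off for the trial team and is not needed to correct the error.

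**What to change.** - **Section 17.1.** Reword so that exclusion of the red zone is claimed for delivery and acceptability as printed, and not for follow-up at the 75% threshold. Say that for follow-up the lower limit lies close to the red boundary.
- **Table 2, follow-up row.** Print the interval at 23/30 (76.7%) and name the method, preferably Wilson (59.1% to 88.2%) or exact (57.7% to 90.1%), with a note that the lower limit falls slightly inside the red zone. If Wald is kept, print 61.5% to 91.8% and name it as such.
- **Leave the delivery row out of this change.** It is worded as a percentage of therapists, overall and by therapy, so its denominator need not be 30 and recomputing it at participant counts would not be apt.

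The cost is one or two sentences and one table cell. The sample size and the progression thresholds stay as they are. The only loss is a slightly less favourable claim for follow-up.

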8. DESIGN

The FReSH START feasibility study is a single arm trial, taking place across four sites, aiming to recruit 30 participants aged 16 years or older and reporting a self-harm episode in the preceding three months that is at least their 3rd episode in the preceding 12 months and their lifetime 4th.

To ensure that our intervention is compatible with NHS practice we will recruit through mechanisms which mirror NHS pathways. Thus we will recruit participants who present to health services – most commonly hospital Emergency Departments (ED), but also adult mental health teams and primary care.

Eligible, consenting participants will be registered and allocated to receive the trial intervention, comprising one of the three psychological therapies modified specifically for use with people who multiply self-harm: Behavioural Therapy/Cognitive Behaviour Therapy (BT/CBT), Psychodynamic Interpersonal Therapy (PIT), and Acceptance and Commitment Therapy (ACT). Delivery of the intervention will be by a therapist recruited and trained in one of the modified psychological therapies for the feasibility trial; therapy (BT/CBT, PIT or ACT), and therapist will be randomly allocated to participants.

Participants will be followed-up for 6 months from registration. Patient reported outcome data will be collected at 6 months post registration via postal or online administration (or telephone if appropriate) and via monthly text alerts for self-reported self-harm episodes. Repetition of self-harm will also be collected directly from hospital electronic records by the researcher during the follow up phase. Details on participant intervention provision and adherence will be recorded. Therapist level data will be collected, including demographics, experience and competencies, training, and ongoing supervision attendance. Fidelity to each of the intervention will be measured, including fidelity to the self-harm adapted approach, and to each of the three psychological therapies (BT/CBT, IPT and ACT). Inclusion of the key ingredients of the self-harm adaptation will be further recorded for the first assessment session of each therapy.

A parallel study will approach a sample of therapists and participants to take part in an interview study to refine the intervention and logic model ahead of the definitive multicentre RCT.

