11.3. Therapist identification

The intervention will be delivered by health professionals (mental health nurses, psychologists, OTs or psychiatrists, counsellors) who have either prior experience of work with people who self-harm and managing risk, or who are trained in one of the three therapies. Some prior experience of delivering any form of recognised therapy is desirable but not essential. Good interpersonal skills are essential as judged by being able to form strong working alliances with clients/users.

Potential therapists will be identified at each site following discussion with the relevant service managers. All therapists will have a recognised mental health professional background (eg. Nursing, occupational therapy, clinical psychology, psychiatry, CBT therapist, counsellor). We aim to recruit two therapists for each type of therapy at each site, with at least two of the three therapies made available at each site.

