15. OUTCOMES

The outcomes relate to intervention delivery, acceptability and feasibility of recruitment, follow-up and outcome data collection, as follows :

Intervention delivery and acceptability

- Number and proportion of therapists undergoing training and deemed competent.
- Therapy delivery by randomly allocated therapist, cross over of patients to therapists.
- Proportion of participants attending therapy, completing the required number of therapy sessions, number of early drop-outs from treatment, reasons for early drop outs, overall and by therapy type (BT, ACT, PIT).
- Availability and uptake of other treatments and services accessed by participants
- Proportion of participants taking up telephone "top up" contact at end of therapy.
- Proportion of participants and therapists delivering key intervention components, overall and by therapy type (BT, ACT, PIT) as recorded by the therapist
- Proportion of treatment sessions by method of delivery
- Participant and therapist fidelity to the intervention including fidelity to the self-harm modifications and to the individual psychological therapeutic approach overall and by therapy type (BT, ACT, PIT) as recorded by the researcher rated audio-recordings.
- Number and attendance of therapy specific supervision sessions.

Recruitment methods, uptake and follow-up

- Number of patients screened for eligibility, overall and by site
- Number of study cards given out and proportion completed, overall and by site
- Method of referral e.g. Emergency Department, self-harm team, clinical staff, general practice.
- Proportion of patients who complete the study card, who could be followed-up by the Researcher to assess eligibility and proportion of those found eligible for the study, overall and by site
- Proportion of patients that consent and are registered to the study out of those found eligible
- Reasons for non-participation, overall and by site
- Proportion of patients completing the study out of those registered, number of withdrawals from follow-up data collection, reasons for withdrawal, overall and by site
- Number of losses to follow-up and characteristics of participants lost to follow-up

Follow-up data collection

- Proportion of participants with available monthly self-reported repetition of self-harm data
- Proportion of participants with 6 month self-reported outcome data, proportion obtained through postal, online, telephone or face to face administration

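### The Delivery criterion in Table 2 counts therapists, overall and by therapy, but its confidence interval is computed for 30 units, the number of participants

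*Protocol*

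**What the plan says.** Section 17.1 justifies the sample size through the progression criteria: "With 30 participants, the 95% CI around our green (go) criteria will exclude values in the red zone". It draws the conclusion for delivery by name: "should we meet the go criteria we can be sufficiently confident that follow-up, delivery and acceptability will not fall to unacceptable levels".

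The Delivery row of Table 2 reads "Delivery: % therapist delivering" key intervention components, to be judged "overall and by each therapy". Red is below 60%, amber 60% to 80%, green above 80%. The interval beside green is "95% Cl: 65.7%, 94.3".

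The number of therapists appears elsewhere. The study is "taking place across four sites" (section 8). Section 11.3 says "We aim to recruit two therapists for each type of therapy at each site", and sections 10.5 and 11.3 require at least two of the three therapies at each site. Section 17.1 itself works with a minimum of two therapists per centre.

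The matching outcome in section 15 uses a different unit: "Proportion of participants and therapists delivering key intervention components, overall and by therapy type (BT, ACT, PIT) as recorded by the therapist".

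**The concern.** A proportion of therapists has the number of therapists as its denominator, and the protocol nowhere plans 30 of them. An interval computed for 30 is then too narrow, and the statement that green excludes red may not hold. Judging the row within each therapy divides a small denominator again.

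This bears on the decision to go on to the definitive trial. The thresholds, the interval and the assurance are fixed in the protocol and are the stated reason why 30 participants are enough. If the assurance does not hold, a green Delivery result could be read as stronger evidence than it is. With few therapists per therapy, the by-therapy result can also move between colours on one therapist's performance.

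**Working it through.** **Inputs.** Green boundary 80%, red below 60%, and 30 participants (section 17.1 and Table 2). Four sites (section 8). Minimum therapists: 2 per centre × 4 = 8 (section 17.1). Target: 2 per therapy × 2 or 3 therapies × 4 sites = 16 to 24 (sections 10.5 and 11.3). Per therapy, assuming a roughly even split over three therapies: 2 or 3 therapists at the minimum and about 5 to 8 at target. Participants per therapy: about 30/3 = 10.

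**Reproducing the printed figure.** The Wald interval is p ± 1.96 × √(p(1−p)/n). With p = 0.80 and n = 30, √(0.16/30) = 0.0730 and 1.96 × 0.0730 = 0.143, giving 65.7% to 94.3%, exactly as printed. The same formula with n = 30 reproduces the Follow-up row (59.5% to 90.5%) and the Acceptability row (53.6% to 86.4%). So the Delivery interval uses the participant count.

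**Same method, planned denominators, at 80%.**

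| Level and unit | n | Wald lower limit | Excludes red (<60%)? |
|---|---|---|---|
| Overall, therapists (minimum) | 8 | 52.3% | no |
| Overall, therapists | 12 | 57.4% | no |
| Overall, therapists | 15 | 59.8% | no |
| Overall, therapists (target, low) | 16 | 60.4% | barely |
| Overall, therapists (target, high) | 24 | 64.0% | yes |
| One therapy, therapists | 3 | 34.7% | no |
| One therapy, therapists | 5 | 44.9% | no |
| One therapy, therapists | 6 | 48.0% | no |
| One therapy, therapists | 8 | 52.3% | no |
| One therapy, participants | 10 | 55.2% | no |

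For example, at n = 16: √(0.16/16) = 0.10, and 80% − 19.6% = 60.4%.

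**Exact (Clopper-Pearson) lower limits at the smallest attainable green count.** Overall: 7/8, 47.3%; 13/16, 54.4%; 20/24, 62.6%. Within a therapy: 3/3, 29.2%; 5/5, 47.8%; 5/6, 35.9%; 7/8, 47.3%; 9/10 participants, 55.5%.

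**Chance of missing green when delivery is good**, assuming independent therapists. With five or fewer therapists in a therapy, above 80% means all of them, since 4/5 is exactly 80% and not green. At a true rate of 90%:

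- 5 therapists per therapy: 0.9⁵ = 0.590 for one therapy; 0.590³ = 0.21 for all three.
- 8 therapists per therapy (7/8 suffices): 8 × 0.9⁷ × 0.1 + 0.9⁸ = 0.383 + 0.430 = 0.813; cubed, 0.54.

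At a true rate of 95% the chance that all three are green is 0.46 (5 each) and 0.84 (8 each).

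**If participants are the unit.** They share therapists, so the effective number is 30/[1 + (30/k − 1) × ICC] for k therapists. The protocol gives no ICC, so a range is assumed. From ICC 0.05 up to 1, the overall Wald lower limit falls from 64.7% to 52.3% with 8 therapists and from 65.4% to 60.4% with 16.

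**The case against.** **The overall assurance survives at target staffing.** A reader might infer that the claimed protection against red is simply false. The documents do not support that for the overall result. Eight therapists is a floor; the target is 16 to 24, and there the protocol's own method keeps the lower limit at 60.4% to 64.0%. This stands, with a qualification. The margin at 16 is 0.4 points, and the exact limit at 13/16 is 54.4%. That last figure reflects a change of method as well as of denominator.

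**80% is not itself green.** At 7/8 the Wald lower limit is 64.6%, which would exclude red even with 8 therapists. This does not help much: the Wald upper limit there is 110.4%, and at 5/5 the Wald interval has no width at all. The method is unreliable at these counts, and the exact limits are below 60% in every by-therapy case shown.

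**The by-therapy rule can be passed.** A reader might infer that it is nearly impossible to pass. The documents do not say that every therapy must be green, nor how overall and by-therapy results combine, and amber lies between. At 95% true delivery all three are green with probability 0.46 to 0.84. At 90%, the chance that any therapy is red is only 2.5% (5 each) or 1.5% (8 each), although it is 23.5% if 8 therapists split 3/3/2. The usual consequence at target staffing is an amber therapy, not a stop.

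**The unit may be participants.** Section 15 mentions both units, so 30 could be the intended denominator. Overall, with 16 therapists, clustering would then leave red excluded. By therapy, about 10 participants still give 55.2% before any clustering.

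**Data source.** Because the section 15 outcome is recorded by the therapist, a reader might infer that the go decision rests on self-report and should move to audio ratings. Table 2 names no source. Researcher-rated fidelity is already a planned outcome, and under section 11.6 the therapy-specific ratings are made by the therapy leads, who train and supervise the therapists, or by their delegates. That is a separate and debatable choice, and this point does not depend on it.

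**Feasibility setting.** No hypothesis is tested and results are reviewed against the criteria rather than applied automatically. True, but the interval and the assurance are the protocol's own argument for its sample size.

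**Conclusion.** The point holds in a limited form. The Delivery interval is computed for the wrong denominator given the row's own wording. Overall, the assurance fails at the stated minimum of 8 therapists, holds by the Wald method from 16, narrowly there, and holds on the exact limit at 24 (62.6%). By therapy it fails on either unit: 34.7% to 52.3% for 3 to 8 therapists, and 55.2% for 10 participants. A therapy with good delivery will often miss green by chance, with all three green about 21% (5 therapists each) to 54% (8 each) of the time at 90% true delivery.

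This rests on therapist totals derived from the stated minimum and target, a roughly even split over three therapies, and independent therapists. It does not show that the overall assurance fails at target staffing, or that the by-therapy criterion cannot realistically be met.

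**What to change.** 1. State in Table 2 and section 15 whether the Delivery unit is the therapist, the participant or the session, and give the planned denominator.
2. Replace the printed interval with one for that number of therapists: exact if therapists are counted, therapist-clustered if participants or sessions are.
3. In section 17.1, limit the statement that green excludes red to the overall Delivery result and to therapist numbers that support it, or withdraw it for Delivery.
4. Apply the traffic light to the overall proportion, and report the by-therapy proportions descriptively with their counts.

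The cost is protocol wording and one recalculated interval, with no extra data collection. The downside is a wider, less favourable interval and no formal go rule for each therapy.

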17.2. General Considerations

Statistical analysis is the responsibility of the CTRU Trial Statistician under the supervision of the Supervising Statistician. The analysis plan outlined in this section will be reviewed and a detailed, final statistical analysis plan will be written before any analysis is undertaken. The analysis plan will be written in accordance with current CTRU standard operating procedures (SOPs) and guidelines and will be finalised and agreed by the following people: the Trial Statistician, the Supervising Statistician, the Chief Investigator, the CTRU Principal Investigator and the Senior Trial Manager. Any changes to the finalised analysis plan and reasons for change will be documented.

